11 ADVERSE EVENT REPORTING

The safety of the device will be monitored throughout the trial by assessment of serious adverse events (SAE), adverse device effects (ADE) serious adverse device effects (SADE), and major adverse events (MAE), or events that may potentially meet an endpoint. All SAEs will be recorded in the eCRF system and will be assessed by the Sponsor. Additionally, applicable events will be assessed by the internal Complaint Handling Department in order to comply with adverse event reporting. Non-serious adverse events with no device relationship that do not meet a trial endpoint, will not be evaluated in this trial (definition according to ISO 14155:2011(E)).

Independent adjudication will occur for all ADEs, MAEs and SADEs reported by the sites within this trial. For any adjudicated events, the adjudicator or designee will be required to complete the eCRF data capture form.

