Independent Adverse Event Review	Independent physician(s) will adjudicate all Major Adverse Events (MAE), Adverse Device Effects (ADE), Serious Adverse Device Effects (SADE) and Unanticipated

-Market I rial August 2021					
Adverse Device Effects (UADE) reported by the sites within this trial. Independent physician(s) will complete the eCRF data capture form for all adjudicated events.					
Available imaging will be evaluated by an independent Core Lab.					
1. Male or female at least 18 years old					
2. Subjects with minimum of 2 years life expectancy					
3. Subjects have signed the informed consent document for data release					
4. Subjects with infrarenal AAA who are assessed by the Investigator to be eligible for endovascular Abdominal Aortic Aneurysm Repair with the trial devices					
Currently participating in another trial where primary endpoint has not been reached yet					
2. Known allergy to any of the device components					
3. Pregnant (females of childbearing potential only)					
4. Subjects with pre-existing EVAR, i.e., in need of repair/intervention of a previously failed EVAR.					
The LEOPARD Trial is designed to compare the anatomically stabilized AFX Endograft System to a reference group of proximally fixated EVAR devices. Patients will be randomized between the two groups.					
Randomization will be 1:1. Each Investigator will select one comparator device of their choice before enrolling the first patient. The trial will sequentially evaluate non-inferiority and superiority hypotheses.					
Randomization Scheme:					
Patient Population per Investigator Reference Group (One Device Selected Prospectively by Each Participating Investigator)					

LEOFAND AAA US FUSI	August 2021					
Primary Endpoint	One year survival in absence of Aneurysm Related Complications. ARC is a composite of the most relevant EVAR outcomes and includes:					
	 Peri-Operative Death (≤ 30-days) Rupture Conversion to OSR Endoleaks; post-operative Migration (≥ 10mm) Aneurysm Enlargement (≥ 5mm) Endograft Limb Occlusions Reinterventions for device- or aneurysm-related complications Any imaging driven observation at 365 days ± 60 days will be included in the one year evaluation window 					

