5.6 ENROLLMENT AND RANDOMIZATION

Patient enrollment into this trial is based on the site evaluation of patient conformance with the protocol-specified selection criteria (see §5.1), and the Investigator's assessment of suitability for treatment with either the AFX-System or the comparator device. Blood work and physical exam will also be collected as per standard of care at each institution.

Once consented and assessed for inclusion in the trial, the Investigator will elect to randomize the patient by entering required information into the EDC. Upon entering this information, the patient will be randomized to receive the AFX® System or the comparator device. The randomization result will be generated and accessible to the site prior to the scheduled procedure date.

Enrollment in the trial only occurs upon advancement of the trial device into the subject's vasculature.

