10.2.3 DATA ANALYSIS

In the original analyses, the ARC endpoint has been evaluated by site reported events only. Now that Corelab data is available, it will be considered during the future evaluations of the data.

In future analyses, the data presented will utilize CoreLab findings in addition to site-reported findings. The analyses will defer to CoreLab results when the site and CoreLab disagree. In the absence of CoreLab-reviewed data, events will be assessed by the site. In addition to this, the clinical data and evaluation of the patients will be considered when reviewing data, and the clinical history of the patient as well as the review of the independent adjudicator may overrule site and Corelab findings.

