11.1 ADVERSE EVENT DEFINITIONS¹

11.1.1 UNANTICIPATED ADVERSE DEVICE EFFECT (UADE)

UADE is any serious adverse effect on health or safety or any life-threatening problem or death caused by or associated with a device, if that effect, problem, or death was not previously identified in nature, severity or degree of incidence. Additionally, an unanticipated adverse event includes any other unanticipated serious problem associated with a device that relates to the rights, safety, or welfare of subjects (US 21 CFR 812.3).

¹ Clinical investigation of medical devices for human subjects, good clinical practice. ISO 14155:2011.

Investigators shall submit to Endologix and to the reviewing ethics committee/IRB a report of any unanticipated adverse device effect occurring during an investigation as soon as possible, but no later than 24-hours after the Investigator first learns of the effect.

Investigators must submit to Endologix documentation of the report made to the ethics committee. NOTE: Planned hospitalization for a pre-existing condition, or a procedure required by the CIP (Clinical Investigation Plan), without serious deterioration in health, is not considered an SAE.

The relation to the investigational device, as well as the relation to the index procedure is classified by the Investigator as either "Related" or "Unrelated".

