13.3 INDEPENDENT EVENT REVIEWER RESPONSIBILITIES

An independent physician(s) will adjudicate all MAEs, ADEs, SADEs and UADEs reported by the sites within this trial. The independent physician will complete the eCRF data capture form for all the adjudicated events.

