13.4 INDEPENDENT CORE LAB RESPONSIBILITIES

All images obtained in this trial will be assessed by an external, independent Core Lab and measurements of the assessment will be recorded in the eCRF, to ensure uniform and unbiased image assessment throughout the trial.

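### Non-fatal ARC events have a stated route to independent adjudication only if the site, knowing the arm, reports them and calls them device-related

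*Combined protocol and SAP*

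**What the plan says.** Section 11 gives the adjudication rule: "Independent adjudication will occur for all ADEs, MAEs and SADEs reported by the sites within this trial". Section 13.3 gives a slightly longer list: "An independent physician(s) will adjudicate all MAEs, ADEs, SADEs and UADEs reported by the sites within this trial". The synopsis matches 13.3; section 11 leaves out UADEs. All three limit the rule to what sites report. Section 11 also names possible endpoint events among those to be monitored, but does not carry them into the adjudication sentence.

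Section 11.1.1 leaves relatedness to the site: the relation to the device, "as well as the relation to the index procedure is classified by the Investigator as either" related or unrelated. On knowledge of the arm, section 5.6 says: "The randomization result will be generated and accessible to the site prior to the scheduled procedure date".

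Under section 13.4 the core lab reads all images and "measurements of the assessment will be recorded in the eCRF". Under section 10.2.3 the core lab prevails where it and the site disagree, the site's assessment stands where there is no core-lab review, and "the review of the independent adjudicator may overrule site and Corelab findings". Section 12.1 refers to an Adjudication Charter for more detail on the ARC definitions.

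**The concern.** ARC decides the non-inferiority test. The adjudicator has the last word on ARC, but the rule that sends events to the adjudicator is written in safety-reporting categories, not endpoint categories. For most ARC components the deciding step is the investigator's view on device relatedness. That view is formed with the arm known, in a comparison of the sponsor's device with a comparator the investigator chose (section 4.5). If the threshold for calling an event related differs between the two devices, the share of ARC events open to the adjudicator's override differs by arm as well.

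There is also a safety side. A finding first seen by the core lab can count in ARC, yet no stated step turns it into an adverse-event entry that would be assessed as an ADE, SADE or UADE.

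**Working it through.** The question is mainly one of reading, so the ARC components in section 6.1 are set against the MAE lists in 6.2 and 12.3, the core-lab role in 13.4 and the trigger in 11 and 13.3. The visible text names ADEs and SADEs without defining them. I take them to be events attributed to the device, in line with the UADE definition and the related/unrelated classification.

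| ARC component | On the MAE list? | Core-lab reading? | Stated route to the adjudicator |
|---|---|---|---|
| Peri-operative death | Yes, through all-cause mortality | Not applicable | Any death the site reports |
| Endoleak, migration, enlargement | No | Yes, where images exist | Only if site-reported and called device-related |
| Limb occlusion | No | When imaged | Same |
| Rupture, conversion | No | Only so far as images show it | Same |
| Reintervention | No | No stated check on its cause | Same |

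Three further comparisons matter.

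1. ARC membership and the trigger use different tests. Under 12.1 a conversion counts whatever the reason, yet a conversion called unrelated has no stated route to the adjudicator. Under 6.1 a reintervention counts only if a complication of the device or aneurysm led to it. The site's view of cause can then settle both whether it counts and whether anyone independent looks at it.
2. Sections 11 and 12.2 disagree on capture. Section 11 drops an event only if it is non-serious, unrelated to the device and not an endpoint event. Section 12.2 says device-unrelated adverse events are not captured at all.
3. Imaging follows each site's standard of care (5.8), so core-lab coverage may be incomplete. Where it is missing, the site's assessment stands (10.2.3).

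Size of the pool, from section 10.2:

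- Evaluable patients: 455 x 0.90 = 409.5, which reproduces the plan's 410, or 205 per arm at 1:1.
- Planned success: 86% for AFX. Reading the 8% advantage as absolute gives 78% for control. This reading reproduces the plan's 566 for superiority with one-sided alpha 0.05 and 80% power: (1.645 + 0.842)^2 x (0.86 x 0.14 + 0.78 x 0.22) / 0.08^2 is about 282.1, rounded up to 283 per arm, 566 in total.
- Expected year-1 failures: 205 x 0.14 + 205 x 0.22 = 28.7 + 45.1 = 73.8, about 74.
- The plan reports that the superiority evaluation was judged futile, so the 8-point advantage may not hold. As an assumed range with equal arms, both at 86% gives 410 x 0.14 = 57.4 and both at 78% gives 410 x 0.22 = 90.2.

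The documents do not give the share of failures that sites would call unrelated, or the share seen only by the core lab. The number without a route to adjudication therefore cannot be calculated.

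**The case against.** A reader might infer that these events are never adjudicated. The documents do not support that. Section 10.2.3 gives the adjudicator power to overrule site and core-lab findings, so some review of endpoint findings is foreseen. The routing could be in the Adjudication Charter or in Figure 2, neither of which is available. The summary of changes says 13.3 was revised to agree with the adjudication plan. That makes a much broader list there less likely but does not exclude it. What stands is that the visible text states no route.

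A reader might also infer that these events escape all independent review. For imaging components that is wrong: the core lab reads every image whatever the site says about relatedness, and it prevails over the site. All deaths are MAEs, not only peri-operative ones. The sponsor assesses all SAEs, and its complaint-handling group assesses applicable events, although neither is independent adjudication.

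The strongest objection is that there is no bias. An unadjudicated event still counts through the core lab or the site, so calling an AFX event unrelated leaves that failure in place. This is right for many events, and it means the direction of any bias cannot be stated. It does not dispose of the point. The override is assured only for events selected by a judgement made with the arm known, and a reintervention whose cause the site attributes elsewhere can leave ARC with no stated independent check.

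Finally, a reader might infer an inflated false non-inferiority rate. That would require events to be lost from ARC. The documents give no loss rate, so no error-rate figure is attached here.

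**Conclusion.** The point holds as a gap in routing. Mandatory adjudication is tied to site reporting and, for every non-fatal ARC component, to a device-relatedness call made by a site that knows the arm. It matters most for reinterventions, conversions, ruptures and any event without core-lab images. For imaging findings seen only by the core lab, the endpoint reading is independent; what is missing is a stated path to the adjudicator and to ADE, SADE or UADE assessment.

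The pool potentially affected is about 74 expected year-1 failures on planned rates (57 to 90 on the equal-arm assumptions). It includes deaths, which are adjudicated when reported, and events that sites will call related. It is not a count of unadjudicated events.

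The conclusion assumes that ADE and SADE mean device-attributed events, that site knowledge of the arm follows from section 5.6 (no blinding of sites to the device is described), and that the unavailable charter and figure do not already supply the route. If they do, sections 11 and 13.3 still need to be brought into line with them.

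**What to change.** - In the synopsis, section 11 and section 13.3, use one identical trigger: *every suspected ARC event, from site or core lab and regardless of the investigator's relatedness assessment, plus all MAEs, ADEs, SADEs and UADEs*.
- In section 13.4, require that a core-lab-positive finding the site has not reported goes to the site as a data query for adverse-event entry, so that it enters the existing reporting pathway.
- Reconcile section 12.2 with section 11 so that endpoint events called device-unrelated are captured.
- Check the Adjudication Charter and Figure 2 against the new wording.

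Section 10.2.3 already changes how ARC is ascertained for future analyses, so the amendment can take effect there. It uses the existing adjudicator, images and eCRF and needs no new visits or imaging. The cost is more case files for the adjudicator and more queries for sites. For the one-year endpoint the pool is on the order of 74 patients; some will already have been adjudicated, but suspected events will outnumber confirmed failures. Applying the rule to ARC through five years costs more. Reported device-event rates may rise slightly.

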11.1 ADVERSE EVENT DEFINITIONS¹

11.1.1 UNANTICIPATED ADVERSE DEVICE EFFECT (UADE)

UADE is any serious adverse effect on health or safety or any life-threatening problem or death caused by or associated with a device, if that effect, problem, or death was not previously identified in nature, severity or degree of incidence. Additionally, an unanticipated adverse event includes any other unanticipated serious problem associated with a device that relates to the rights, safety, or welfare of subjects (US 21 CFR 812.3).

¹ Clinical investigation of medical devices for human subjects, good clinical practice. ISO 14155:2011.

Investigators shall submit to Endologix and to the reviewing ethics committee/IRB a report of any unanticipated adverse device effect occurring during an investigation as soon as possible, but no later than 24-hours after the Investigator first learns of the effect.

Investigators must submit to Endologix documentation of the report made to the ethics committee. NOTE: Planned hospitalization for a pre-existing condition, or a procedure required by the CIP (Clinical Investigation Plan), without serious deterioration in health, is not considered an SAE.

The relation to the investigational device, as well as the relation to the index procedure is classified by the Investigator as either "Related" or "Unrelated".

11.2 SERIOUS ADVERSE EVENTS (SAE)

Per ISO 14155, a SAE is a serious adverse event that

- a) Led to death,
- b) Led to serious deterioration in the health of the subject, users or other persons as defined by one or more of the following:
 - 1) A life-threatening illness or injury, or
 - 2) A permanent impairment of a body structure or body function, including chronic diseases, or
 - 3) In-patient or prolonged hospitalization, or
 - 4) Medical or surgical intervention to prevent life-threatening illness or injury or permanent impairment to a body structure of a body function,
- c) Led to fetal distress, fetal death or a congenital abnormality or birth defect, including physical or mental impairment.

The Investigator must report any SAE in the eCRF to Endologix, Inc. as soon as they become aware of the event, preferably within 24-hours of awareness of the event. Refer to Figure 2 for the decision tree for event reporting:

[figure not shown]

Figure 2: Reporting Decision Tree

12 DEFINITIONS

12.1 DEFINITIONS ASSOCIATED WITH THE COMPOSITE PRIMARY ENDPOINT ARC

The primary trial endpoint is an assessment at one year, where survival is in the absence of Aneurysm Related Complications (ARC). ARC is a composite of the most relevant EVAR related outcomes and include:

- *Aneurysm Rupture*: bleeding or leaking of blood from the aneurysm subsequent to the index procedure.
- Conversion to Open Surgical Repair (OSR): open surgical repair of the abdominal aortic aneurysm due to unsuccessful delivery or deployment of the stent graft, due to complications or other clinical situations that precluded successful endovascular treatment, or at any time following initial successful endovascular treatment for any reason. Excludes post-mortem explant of the trial device.
- Endoleaks: clear evidence of contrast within the aneurysm sac
 - **Endoleak Type Ia** Contrast material in the aneurysm sac adjacent to the proximal seal zone and/or between the endograft and the inner wall of the proximal attachment site.
 - **Endoleak Type Ib** Contrast material in the aneurysm sac adjacent to the distal seal zone and/or between the endograft and the inner wall of the distal attachment site.
 - **Endoleak Type II** Contrast material along the posterior sac wall with visualization of lumbar artery or the inferior mesenteric artery

LEOPARD AAA US Post-Market Trial

- Endoleak Type IIIa Component disconnect
- Endoleak Type IIIb Mid-graft hole
- *Migration* (≥10mm): stent distal movement ≥10mm from the original implant location relative to the center of the distal renal artery; as compared to the 1-month CT scan location.
- Aneurysm Sac Enlargement: aneurysm sac diameter increase of ≥5mm in late followup as compared to 1-month CT scan location.
- *Endograft Limb Occlusions*: defined as total obstruction of blood within the lumen of a device limb irrespective of whether a secondary intervention is necessary.
- *Endograft Stenosis:* defined as a reduction in lumen >50% by, for example, thrombus, intimal hyperplasia, or endograft kink/twist.

Elaboration of the above definitions can be found in the Adjudication Charter.

12.2 ADVERSE EVENT DEFINITIONS

An adverse event (AE) is defined as any untoward medical occurrence, unintended disease, injury or untoward clinical sign (including abnormal laboratory values) in subjects, users or other persons, whether or not related to the medical device (ISO 14155). For the purposes of this study, adverse events that are not related to the study device will not be captured as shown in **Figure 2**.

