12.3 MAJOR ADVERSE EVENT

An event occurring during the trial that meets one of the following criteria:

- *All-Cause Mortality*:
- Death is defined as any death occurring during the trial period, regardless of cause.
 - O Aneurysm-related death: is defined as any death occurring within 30-days from the date of the index procedure, regardless of cause, and death due to aneurysm rupture or death within 30-days of any secondary procedure intended to treat the aneurysm.
 - o Cardiac-related death: is defined as death due to arrhythmia, heart failure (including cardiogenic shock), or myocardial infarction
 - o *Pulmonary-related death:* is defined as death due to due to pulmonary edema, respiratory failure, or pulmonary embolism
 - Vascular-related death: is defined as death due to stroke, cerebral hemorrhage, or other clear vascular event that is not categorized as cardiac-related or pulmonary-related or aneurysm-related.
 - o *Other:* is to be used to identify a death due to any event that cannot be clearly categorized as above, but where some information is available.
 - o *Unknown*: is to be used to identify a death where no information is available.
- *Bowel Ischemia:* the lack of adequate blood flow to the intestines that requires intensification of medical therapy or surgical/endovascular intervention.

- Myocardial Infarction: increase of one or more cardiac biomarkers (preferably troponin) with at least one value above the 99th percentile of the upper reference limit (URL) together with evidence of myocardial ischemia with at least one of the following: myocardial ischemia; ECG changes indicative to new ischemia (new ST-T changes or left bundle branch block (LBBB)); development of pathological Q-waves in the ECG; imaging evidence of new loss of viable myocardium or new regional wall motion abnormality.
- Paraplegia: paralysis of the lower extremities inclusive of the lower trunk;
- Renal Failure permanent dialysis dependence or kidney transplant
- Respiratory Failure: respiratory failure requiring ventilator support beyond 24 hours post-procedure
- *Stroke:* a sudden development of neurological deficit due to vascular lesions of the brain such as hemorrhage, embolism, or thrombosis that persists for >24 hours;
- *Index Procedural Blood Loss* >1,000mL: estimated blood loss during the index procedure ≥1,000mL.

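### Section 12.2 excludes every device-unrelated adverse event, which conflicts with the all-SAE rule and, if followed literally, could leave all-cause deaths and MAEs unrecorded

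*Combined protocol and SAP*

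**What the plan says.** Section 12.2 first defines an adverse event without regard to device relationship, following ISO 14155. It then limits collection for this trial: "adverse events that are not related to the study device will not be captured", with a reference to Figure 2. The sentence makes no exception for serious events, MAEs, deaths or endpoint events.

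Section 11 sets a different rule. It states that "All SAEs will be recorded in the eCRF system and will be assessed by the Sponsor". Its list of monitored events extends to "major adverse events (MAE), or events that may potentially meet an endpoint". Its only exclusion has three conditions: "Non-serious adverse events with no device relationship that do not meet a trial endpoint, will not be evaluated in this trial".

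Section 11.2 requires the Investigator to report any SAE. Death is the first SAE criterion, and Figure 2 is introduced there as the reporting decision tree.

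Section 6.2 makes MAEs at 30 days, 12 months and annually to five years the first secondary endpoint, with all-cause mortality at the head of the list. Section 12.3 matches this: "Death is defined as any death occurring during the trial period, regardless of cause".

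On who decides relatedness, section 11.1.1 says "The relation to the investigational device, as well as the relation to the index procedure is classified by the Investigator".

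**The concern.** Section 12.2 keeps one of section 11's three conditions, device-unrelatedness, and drops the other two. As worded, it excludes events that section 11 requires and that a named endpoint counts whatever their cause.

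Three features of the plan make this more than a drafting slip.

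- Device relation and procedure relation are classified separately. A stroke caused by the procedure but not by the graft would fall inside the 12.2 exclusion.
- Adjudication under sections 11 and 13.3 covers events that the sites report. It cannot recover an event that was never entered.
- Under section 5.6 the site can see the allocation before the procedure. The person judging relatedness therefore knows the arm, and any difference between arms in those calls would pass into the comparison of MAE rates.

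An unentered event also leaves no trace. Section 10.2.2 promises counts of missing values, but a death or MAE that was never entered need not appear as a missing value. The subject can simply look event-free.

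**Working it through.** The plan gives no figure to reproduce here. The check is to apply each rule, as worded, to the same kinds of event.

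| Event, judged unrelated to the device | Section 11 | Section 11.2 | Section 12.2, literal |
|---|---|---|---|
| Death | Recorded (SAE, and an MAE) | Must be reported | Not captured |
| Serious MAE, such as stroke or myocardial infarction | Recorded | Must be reported | Not captured |
| MAE that meets no SAE criterion (possible, for example, for procedural blood loss at the MAE threshold) | Kept, because it meets an endpoint | No duty | Not captured |
| SAE outside the MAE list | Recorded | Must be reported | Not captured |
| Non-serious event meeting no endpoint | Set aside | No duty | Not captured |

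The rules agree only in the last row. In the other four, sections 11 and 12.2 give opposite instructions, and in three of those section 11.2 sides with section 11.

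**Figure 2.** Sections 11.2 and 12.2 both cite it, and it is not visible in the text available. There are two cases. If it follows 12.2, it contradicts sections 11 and 11.2. If it follows section 11, the sentence in 12.2 misdescribes it. Text has to change in either case, so the finding of a conflict does not depend on the figure. What sites were actually told may depend on it.

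**Size.** Let *s* be the share of MAEs judged device-related. A literal 12.2 would drop the share 1 − *s*. The documents give neither *s* nor an MAE rate. More than half would be lost only if *s* < 0.5, and nothing in the plan establishes that. Among deaths, a literal reading would drop every one judged device-unrelated, but the plan does not say how many to expect.

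**Timing.** The synopsis puts enrollment completion at Q3 2017. Adding 12 months gives Q3 2018, and the 60-day imaging window takes this to about Q4 2018. Revision 02 is dated 29 August 2021, and its change log lists sections 11 and 12.2 among those revised. Five-year follow-up was due to complete in Q4 2022. The present 12.2 wording can therefore have governed only late follow-up and later data cleaning, unless Revision 01 said the same, which the documents do not show.

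**The case against.** The strongest reply is that the rest of the protocol protects these events. Section 11.2 uses mandatory language for any SAE, section 11 keeps all SAEs and potential endpoint events, section 12.3 counts death whatever the cause, and section 13.3 adjudicates reported MAEs with no relatedness filter. Most listed MAEs would ordinarily qualify as SAEs. A site would have to let one sentence in a definitions section override an express duty. That sentence also refers to Figure 2, which may carry branches for SAEs and endpoint events.

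Much of this stands. Read together, the sections do not order the loss of these events; they give conflicting instructions, and the weight of the text favours full capture. The reply does not remove the conflict, because 12.2 is current text and states its exclusion without limits.

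Two stronger readings are tempting, and the documents support neither.

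- A reader might infer that most MAEs would be lost. That needs a device-related share that the plan does not give, and it needs sites to have followed 12.2 over section 11.2.
- A reader might infer that a countable number of deaths is missing from the primary endpoint. The ARC list in section 6.1 names only peri-operative death. Whether a later non-aneurysm death is a primary failure is a separate ambiguity. One-year follow-up had also largely ended before Revision 02. An effect on the primary endpoint is possible but not shown.

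**Conclusion.** The contradiction is certain on the text. Section 12.2 omits two limits that section 11 states, and it conflicts with the all-SAE rule, with the duty to report any SAE including death, and with the all-cause MAE and mortality endpoint. It is a wrongly worded rule rather than missing detail, and nothing suggests a deliberate decision to drop all-cause events.

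The consequence is conditional. Device-unrelated deaths and MAEs are lost only where a site, or whoever cleans the data, applied 12.2 in preference to sections 11 and 11.2. No number can be put on this from the documents. The clearest exposure is late MAEs and mortality collected or cleaned under Revision 02. The point should be settled before lock, because an unentered event cannot be detected from the database alone.

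**What to change.** Reword 12.2, and check Figure 2, so that both agree with sections 11 and 11.2. The rule should be that all deaths, SAEs, MAEs, ADEs and events that may meet an endpoint are recorded whatever their relatedness, and that only non-serious, device-unrelated events meeting no endpoint are not captured.

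Before database lock, send one round of queries to all sites through the existing monitoring. Ask for deaths, MAEs and reinterventions that were not entered because they were judged unrelated. Send recovered events that fall within the adjudication remit to the independent adjudicator, and report the number recovered by arm. If none is found in either arm, that result supports the completeness of the MAE and mortality endpoint.

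The cost is one sentence, a check of one figure and one query round. No visit or procedure is added.
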